3.7 Baseline assessment/screening

During the assessment visit, which will occur during the one month period prior to MSC administration, a discussion of the informed consent and signing of the consent will be completed prior to the initiation of study procedures. Medical and surgical history, physical examination and labs will also be performed. To satisfy enrollment criteria, a colonoscopy or flexible sigmoidoscopy, or MR enterography, must have been performed within the preceding 2 months for clinical purposes to document active inflammation. If possible, endoscopic assessment using the SES-CD for CD and the Mayo Score (see appendix 4) will be performed. An upper endoscopy with biopsies may also be performed if the physician deems this necessary for clinical assessment. These procedures may be done for clinical purposes at an outside facility, in which case endoscopic scores may not be available.

3.8 Treatment Phase (Day 0, 7, 14, 21)

On Days 0, 7, 14, and 21, subjects will arrive at the hospital for infusion of study drug, eligibility criteria, laboratory assessments, assessment of AEs/SAEs, collection of serum, saliva, urine and stool, and assessment of clinical indices.

Safety Monitoring Phase (Day 28, 45, 56, 73) +/- 3 days

During this visit, the patient will return to Children's National, or be seen by a local physician for a follow-up visit, physical exam, laboratory assessments, AEs/SAEs assessment, assessment of clinical indices, bloodwork, saliva, urine and stool collected for fecal calprotectin. Assessment of symptoms and screening for adverse events may be done by telephone if necessary.

Follow-up Phase (Day 180, 360, 720) +/- 28 days

Subjects will return to Children's National, or be seen by a local physician, for a physical examination and assessment of clinical indices. If physical examination is obtained by a local physician, reports will be emailed or faxed to the study investigator. Assessment of symptoms and screening for adverse events may be done by telephone if necessary.

3.9 Study Procedures

Any procedures performed during this study, such as endoscopy, colonoscopy, or MR enterography, will be done for clinical purposes.

3.9.1 Phlebotomy

Research blood will be drawn during screening visit, treatment phase, and safety monitoring phase but will not exceed 2 cc/kg or a maximum of 40 ml per blood draw.[53] Blood tests run (CBC, CMP, CRP) are considered standard of care. However, additional tissue specimens (urine, saliva, blood, and stool) may be collected and banked, if the subject provides consent.

Any remaining specimens that will be stored for future research will be stored safely and securely in a research specimen storage laboratory at the CETI Laboratory at CNMC.

4 POTENTIAL RISKS AND BENEFITS

4.1 Allogeneic BMSC Infusion

To date, serious complications or side effects from MSC infusions have not been described. In the trial by Forbes, et al., of MSCs in the treatment of adults with luminal CD, there was one SAE reported: a subject diagnosed with sigmoid adenocarcinoma at the day 42 endoscopy. The patient was subsequently found to have had low-grade dysplasia on sigmoid mucosal biopsy specimen from the entry endoscopy and there had been a previous recommendation for colectomy because of mucosal atypia within a known proximal rectal stricture. [54] Reported infusion side effects are mild and include headache, hives, fever, congestion, and dysgesia (altered taste). Transfusion reactions and allergic reactions have not been reported in published Phase 1 and II trials.

4.2 Phlebotomy

Blood draws may cause pain and bruising. Sometimes drawing blood causes people to feel lightheaded, and very occasionally causes fainting.

4.3 Possibility of Direct Benefit

Subjects may or may not receive any direct benefit from participating in this study. Subjects may potentially have a decrease in active IBD symptoms, possible induction of remission, and possible improved quality of life. Study medications and study-related routine clinical monitoring tests will be provided free of charge. Results of any specialized tests done as part of the study will be made available to interested study subjects, their parents, and their healthcare providers.

5 DRUG TOXICITY AND/OR ADVERSE REACTIONS (AES)

Adverse events will be collected as per SOP BMT_SOP003_AE Routine and serious adverse events will be collected and reported as per SOP BMT_SOP_004_SAE Report.

5.1 ADVERSE EVENT

An AE, as defined by the ICH guideline for GCP, is:

Any untoward medical occurrence in a patient or clinical investigation subject administered a pharmaceutical product and which does not necessarily have a causal relationship with this treatment.

Suspected adverse reaction means any adverse event for which there is a reasonable possibility that the drug caused the adverse event. For the purposes of IND safety reporting, "reasonable possibility means there is evidence to suggest a causal relationship between the drug and the adverse event. Suspected adverse reaction implies a lesser degree of certainty about causality than adverse reaction, which means any adverse event caused by a drug."

An AE is considered to be any adverse change or exacerbation from a baseline condition which occurs following the initial administration of an investigational product whether or not the event is considered to be related to the investigational product. Examples of this include but are not limited to the following:

- Adverse changes including new signs and symptoms, intercurrent illness modifying the clinical course, or the worsening of a baseline condition including the increased frequency of an event or an increased intensity of a condition
- Concomitant disease with onset or increased severity after the start of study product administration
- A new pattern in a pre-existing condition, occurring after the receipt of investigational product that may signal a clinically meaningful change
- Clinically significant changes in laboratory values

5.2 SERIOUS ADVERSE EVENT

As defined by the Code of Federal Regulations (CFR), a serious adverse event (SAE) is any adverse drug experience occurring at any dose that results in any of the following outcomes:

- Death
- Life-threatening adverse event
- Inpatient hospitalization or prolongation of existing hospitalization
- Persistent or significant incapacity or substantial disruption of the ability to conduct normal life functions
- Congenital anomaly/birth defect.

An adverse event or suspected adverse reaction is considered "life-threatening" if, in the view of either the investigator or sponsor, its occurrence places the patient or subject at

immediate risk of death. It does not include an adverse event or suspected adverse reaction that, had it occurred in a more severe form, might have caused death.

Important medical events that may not result in death, be life-threatening, or require hospitalization may be considered serious when, based upon appropriate medical judgment, they may jeopardize the subject and may require medical or surgical intervention to prevent one of the outcomes listed in this definition. Examples of such medical events include allergic bronchospasm requiring intensive treatment in an emergency room or at home, blood dyscrasias or convulsions that do not result in inpatient hospitalization, or the development of drug dependency or drug abuse.

5.3 UNEXPECTED ADVERSE EVENT

As defined by 21 CFR 312.32 (a), an unexpected adverse drug experience is:

"An adverse event or suspected adverse reaction is considered "unexpected" if it is not listed in the investigator brochure or is not listed at the specificity or severity that has been observed; or, if an investigator brochure is not required or available, is not consistent with the risk information described in the general investigational plan or elsewhere in the current application, as amended. For example, under this definition, hepatic necrosis would be unexpected (by virtue of greater severity) if the investigator brochure referred only to elevated hepatic enzymes or hepatitis. Similarly, cerebral thromboembolism and cerebral vasculitis would be unexpected (by virtue of greater specificity) if the investigator brochure listed only cerebral vascular accidents. "Unexpected," as used in this definition, also refers to adverse events or suspected adverse reactions that are mentioned in the investigator brochure as occurring with a class of drugs or as anticipated from the pharmacological properties of the drug, but are not specifically mentioned as occurring with the particular drug under investigation."

5.4 OTHER ADVERSE EVENT

Other adverse events will be identified by the PI during the evaluation of safety data. Significant adverse events of particular clinical importance, other than SAEs and those AEs leading to discontinuation of the subject from the study, will be classified as other adverse events. For each, a narrative may be written and included in the clinical study report.

5.5 RELATIONSHIP TO TREATMENT

The PI or Sub-I must assign a relationship of each AE to the receipt of the investigational product. The investigator will use clinical judgment in conjunction with the assessment of a plausible biologic mechanism, a temporal relationship between the onset of the event in relation to receipt of the investigational product, and identification of possible alternate etiologies including underlying disease, concurrent illness or concomitant medications. The occurrence of adverse events will be monitored at each

visit. The following guidelines should be used by investigators to assess the relationship of an AE to study product administration:

Not related: No relationship to study treatment. Applies to those events for which evidence exists that there is an alternate etiology. For example, events that are clearly related to another medical condition (i.e. diabetes), are related to an outside circumstance (i.e. trauma), or that are not temporally related to administration of the treatment.

Unlikely: Likely unrelated to the study treatment. Likely to be related to factors other than study treatment, but cannot be ruled out with certainty. The need for medical or surgery related to progressive IBD, or known symptoms directly related to IBD such as diarrhea, perianal disease, intra-abdominal or perianal abscess, intra-abdominal fistula, rectal bleeding, and weight loss are unlikely to be related to the study treatment. This also includes patients with known history of extraintestinal manifestations related to IBD (such as arthralgias, arthritis, uveitis, erythema nodosum, pyoderma gangrenosum, or mouth ulcers) who experience such symptoms during the treatment period.

Possible: An association between the event and the administration of study treatment cannot be ruled out. There is a reasonable temporal association, but there may also be an alternative etiology such as the subject's clinical status or underlying factors including other therapy. This includes known potential risks of IBD and treatments that the patient is receiving, such as infection and lymphoma

Probable: There is a high degree of certainty that a relationship to the investigational product exists. There is a reasonable temporal association, and the event cannot be explained by known characteristics of the subject's clinical state or factors including other therapy.

Definite: An association exists between the receipt of investigational product and the event. An association to other factors has been ruled out.

5.6 INFUSION-RELATED ALLERGIC REACTIONS

The investigators should ensure that appropriate best clinical practices and treatment are initiated should an event indicating an allergic or hypersensitive reaction occur. Each event will be recorded as an AE or SAE, depending on which criteria are met by the event. The start and stop/restart times must be recorded in the CRF.

Should an infusion-related allergic reaction occur the infusion will be stopped immediately and the subject closely monitored until stable. An infusion-related allergic reaction may appear as flushing, sudden rash, or shortness of breath or difficulty breathing.

Definitions and grading will follow the current NCI-CTCAE criteria. Current definition and suggested treatment plan for infusion-related allergic reaction:

Grade 1: Mild transient reaction

1. Stop infusion and evaluate for severity. If reaction remains a grade 1 then restart at reduced rate.
2. Reduce infusion rate by 50%,
3. Treat subject per good clinical practice (suggest antihistamines, corticosteroids, etc. as medically indicated) and monitor for worsening condition.
4. If the reaction persists or worsens the infusion will be discontinued.

Grade 2: Readily responds to clinical treatment (e.g., antihistamines, corticosteroids); should consider prophylactic treatment for ≤24 hours.

1. Stop infusion for up to 3 hours (product should not be infused after 4 hours).
2. Administer clinical treatment for allergic reaction as medically indicated.
3. Resume infusion at 50% of previous rate once reaction has decreased to Grade 1 in severity. Monitor closely for any worsening.
4. If the reaction reoccurs, stop infusion. Study treatment is to be discontinued.

Grade 3: Prolonged or severe reaction (e.g., not rapidly responsive to treatment or a recurrence of reaction after an initial improvement of a Grade 1 or Grade 2 reaction.

1. Discontinue infusion immediately. Study treatment is to be discontinued
2. Administer clinical treatment for allergic reaction as medically indicated.
3. Report as a SAE

Grade 4: Characterized as life-threatening AE; urgent intervention indicated to maintain hemostasis.

1. Discontinue infusion immediately. Study treatment will be discontinued.
1. Administer clinical treatment for allergic reaction as medically indicated.
2. Report as a SAE

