- MSC's will be administered intravenously via a 18 gauge needle at a controlled rate of 4-6 ml/minute via infusion pump for patients weighting 35 kg or more. For patients under 35 kg in weight, the infusion will run in over 60 minutes at a rate no greater than 4-6 ml/minute. A syringe in combination with syringe pump can be used for administration in smaller patients.
- During the administration, the infusion must be stopped for any of the following reasons:
 - If the patient has symptoms or signs of respiratory difficulty, including but not limited to tachypnea, cyanosis, complains of shortness of breath, even if the pulse oximeter reading is normal. If the symptoms resolve within 30 minutes after standard supportive oxygen therapy, the infusion may be resumed at half the initial rate and the infusion must be completed within 2 hours of starting the infusion. If the symptoms recur, then the infusion will be stopped and will not be resumed.
 - If SaO_2 decreases to $\leq 90\%$ over a continuous period of > 3 minutes, whether or not the patient has symptoms of respiratory distress. If the SaO_2 is $\leq 90\%$ in the absence of symptoms or signs, the accuracy of the pulse oximeter reading should be confirmed by using another machine, relocating the sensor, or testing the device on another patient.
 - Infusion may be stopped at the discretion of the treating physician if there is another AE that the treating physician believes is related to the infusion, or if there is an issue with the infusion, or if the patient withdraws consent.

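### For an infusion reaction with breathing symptoms, sections 3.1 and 5.6 give conflicting restart and timing rules, and neither says which prevails

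*Protocol*

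**What the plan says.** **Section 3.1 (Preparation Administration, and Dosage).** The infusion has to be stopped for signs or symptoms of respiratory difficulty, including when a patient "complains of shortness of breath, even if the pulse oximeter reading is normal". There is no grade threshold and no exception for an allergic cause. The restart condition is: "If the symptoms resolve within 30 minutes after standard supportive oxygen therapy, the infusion may be resumed at half the initial rate". A time limit follows: "the infusion must be completed within 2 hours of starting the infusion". If symptoms return, that infusion is stopped for good.

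**Section 5.6 (Infusion-Related Allergic Reactions).** The definition overlaps: "An infusion-related allergic reaction may appear as flushing, sudden rash, or shortness of breath or difficulty breathing". The steps by grade are offered as a suggested plan.

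- Grade 1: "If reaction remains a grade 1 then restart at reduced rate". No pause length is given. A later step discontinues the infusion if the reaction persists or worsens.
- Grade 2: "Stop infusion for up to 3 hours (product should not be infused after 4 hours", and then "Resume infusion at 50% of previous rate once reaction has decreased to Grade 1 in severity". On recurrence: "If the reaction reoccurs, stop infusion. Study treatment is to be discontinued".
- Grade 3: treatment is discontinued and the event is reported as an SAE. The examples include prolonged reactions and recurrence after improvement of a Grade 1 or 2 reaction.

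Neither section mentions the other or states an order of precedence.

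**The concern.** A patient who becomes breathless during an infusion, with an allergic cause suspected, falls under both sections. Staff following 3.1 would restart only after symptoms had cleared in time, and would abandon the infusion if it could no longer finish within 2 hours. Staff following the Grade 1 or Grade 2 steps of 5.6 could restart cells while the patient still has mild breathing symptoms. They could also restart after a stop so long that the 2-hour limit has already passed.

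Respiratory difficulty is the first mandatory stopping reason in 3.1, and safety and tolerability is the primary objective. Section 5.6 is the plan arranged by grade that staff would naturally open for an allergic reaction, so the looser rule could well be the one used at the bedside.

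**Working it through.** The protocol gives no figure of its own to reproduce. The check is a comparison of the two texts plus timing arithmetic.

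**Step 1. The two rules side by side, for breathing symptoms of Grade 1 or 2**

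| Point | Section 3.1 | Section 5.6 |
|---|---|---|
| Force | Mandatory | Suggested plan |
| State at restart | Symptoms cleared, within 30 minutes | Grade 1: may still be Grade 1. Grade 2: down to Grade 1 |
| Rate after restart | Half | Half |
| Longest stop | None stated; bounded by the 2-hour total | Grade 2: 3 hours. Grade 1: none stated |
| Total time | 2 hours from start | Outer limit of 4 hours, starting point not stated |

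The sections agree on the rate. They differ on the state of the patient at restart and, for Grade 2, on time.

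**Step 2. Inputs for the timing check**

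- T = planned minutes at full rate. Section 3.1 sets T = 60 for patients under 35 kg. At 35 kg or more the rate is 4-6 mL/min; at 4 mL/min, the 40-120 mL range stated in 3.1 gives T = 40/4 = 10 to 120/4 = 30.
- t = minutes infused before the stop.
- p = length of the pause in minutes.
- The remainder runs at half rate, so it takes 2(T − t) minutes.

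Total time = t + p + 2(T − t).

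**Step 3. The full Grade 2 stop against the 2-hour limit**

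With p = 180, the total exceeds 180 for any t and T. The pause alone passes 120 by 180 − 120 = 60 minutes. This does not depend on infusion length or on how the 4 hours are counted.

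**Step 4. The pause that the 2-hour limit allows**

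Setting the total to at most 120 gives p ≤ 120 − 2T + t.

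| T | t | Longest pause under the 2-hour limit | Total with p = 180 |
|---|---|---|---|
| 60 | 15 | 120 − 120 + 15 = 15 | 15 + 180 + 90 = 285 |
| 60 | 30 | 120 − 120 + 30 = 30 | 30 + 180 + 60 = 270 |
| 30 | 0 to 30 | 60 to 90 | 240 to 210 |
| 10 | 0 to 10 | 100 to 110 | 200 to 190 |

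If the 4 hours in 5.6 run from the start of the infusion, they shorten the permitted pause for T = 60 to 240 − 15 − 90 = 135 minutes (t = 15) or 240 − 30 − 60 = 150 minutes (t = 30). These are still far above 15 and 30.

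**Step 5. When the restart conditions conflict**

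Apart from timing, they conflict in two situations: breathing symptoms are still present at restart, or they cleared only after 30 minutes. In the second case the bar on restarting is implied by the condition in 3.1, not stated outright. If symptoms cleared within 30 minutes, only the 2-hour limit can still be breached.

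**The case against.** The strongest reply is that the text already suggests an order. Section 3.1 is specific to breathing symptoms and mandatory. Section 5.6 is general and only suggested. Staff who follow 3.1 breach no time limit in 5.6, so both can be satisfied at once. This stands as far as it goes: the rules are not impossible to follow together. But the protocol never states the order, and a reader of 5.6 alone is not sent to 3.1.

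Section 5.6 also has safeguards. It calls for an immediate stop with monitoring until the patient is stable, and a long reaction could be regraded as prolonged, hence Grade 3. Stable is not the same as free of symptoms, however. Prolonged has no stated duration, and Grade 2 expressly allows up to 3 hours. The Grade 1 step that ends the infusion if the reaction persists comes after the restart in the sequence.

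Some stronger readings are tempting and are not supported.

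- *Section 3.1 forbids every pause over 30 minutes.* It does not. The 30 minutes limit the time for symptoms to clear. For short infusions, the 2-hour limit allows pauses of 60 to 110 minutes (Step 4).
- *Every Grade 1 respiratory reaction conflicts.* It does not. A mild, transient reaction that has cleared in time before the restart meets the 3.1 restart condition.
- *A probability can be put on the conflict occurring.* The protocol gives no reaction rate. Section 4.1 says that allergic reactions have not been reported in published Phase 1 and 2 trials, and 3.1 includes premedication. Any percentage would rest on an invented rate.
- *Recurrence after a Grade 2 reaction is a second contradiction.* This is weak. Both grades discontinue treatment, and Grade 3 already lists recurrence. Only the SAE instruction is missing from the Grade 2 step.

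**Conclusion.** The conflict is real but limited to Grade 1 and 2 infusion reactions with respiratory symptoms. On restart, it arises when symptoms are still present or took more than 30 minutes to clear. On time, it concerns Grade 2: the permitted 180-minute stop exceeds the 120-minute limit by 60 minutes on its own. Under 35 kg, with a stop at 15 or 30 minutes, that pause gives totals of 285 or 270 minutes where 120 are allowed.

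The 60-minute excess needs no assumption. The worked totals assume that the remainder runs at exactly half rate after a single stop. Flushing or rash alone is unaffected, and no claim is made about how often the situation will occur. Because it loosens a mandatory respiratory limit in a safety study and is easily corrected, it should be fixed.

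**What to change.** Add to section 5.6 that any Grade 1 or 2 reaction with respiratory symptoms follows the limits in 3.1: symptoms cleared within 30 minutes, restart at half rate, and completion within 2 hours of the start. State that the 3-hour stop applies only to reactions without respiratory symptoms.

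As a minor clarification, have item 4 of the Grade 2 steps refer to Grade 3 and SAE reporting when a reaction recurs, as the Grade 3 text already implies.

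The cost is protocol wording and a few abandoned infusions that 5.6 would have let resume.

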5.7 Severity Assessment

All AEs will be assessed for severity by the investigator. Inherent in this assessment is the medical and clinical consideration of all information surrounding the event including any medical intervention required. Each event will be assigned one of the following categories: mild, moderate, severe, or life-threatening. The criteria below may be used for any symptom not included in the grading scale. Any grade 4 (life-threatening) AE must be reported as an SAE.

Mild	Grade 1	Does not interfere with routine activities Minimal level of discomfort
Moderate	Grade 2	Interferes with routine activities Moderate level of discomfort

Severe	Grade 3	Unable to perform routine activities Significant level of discomfort
Potentially life-threatening	Grade 4	Hospitalization or ER visit for potentially life-threatening event

FDA guidelines for toxicity will be followed; however, if a subject is evaluated in an emergency room for nonlife threatening illness or symptoms (i.e., visits emergency department on weekend for mild problems because the physician's office is closed), the information from that visit will be reviewed and severity of the adverse event will be assessed according to the subject's clinical signs and symptoms.

The term "severe" is often used to describe intensity (severity) of a specific event (as in mild, moderate, or severe myocardial infarction); the event itself however, may be of relatively minor medical significance (such as severe headache). This is not the same as "serious", which is based on subject/event outcome or action criteria usually associated with events that pose a threat to a subject's life or functioning. Seriousness (not severity) serves as a guide for defining regulatory reporting obligations.

